4.2 SCIENTIFIC RATIONALE FOR STUDY DESIGN

Justification for an unblinded study: Because it will be clear to both study personnel and participants who is receiving 5 vs. 10 treatments, neither will be blinded in this study. This will be reported as a limitation of the study.

Justification for an uncontrolled study with no control group: Because there is already evidence that acupuncture treatment improved headache-related quality of life and reduced headache pain in individuals suffering from CPTH²⁰, the goal of this study was to provide treatment to both groups and to determine whether a low or high dose of treatment is more effective.

4.3 JUSTIFICATION FOR INTERVENTION

Acupuncture is a treatment that has been practiced for over 4,000 years and is well-accepted by many cultures. Although the mechanism is not well understood, acupuncture has been shown to be safe and effective at treating headaches and migraines. The number of treatments will be examined to determine whether 5 or 10 treatments is more effective at treating CPTH. The 30-minute treatment duration was based on clinical practice guidelines for acupuncture treatment.

4.4 END-OF-STUDY DEFINITION

A participant is considered to have completed the study if he or she has completed study/treatment visits and assessments. Study withdrawals are described in **Section 7**. The end of the study is defined as completion of the 12-week post-treatment visit shown in the Schedule of Activities, **Section 0**.

5 STUDY POPULATION

5.1 INCLUSION CRITERIA

In order to be eligible to participate in this study, an individual must meet all of the following criteria:

- Ability to provide and provision of signed and dated informed consent form
- Age 18-70
- Diagnosis of mTBI (as defined by ICHD-3; a. Either no loss of consciousness, or loss of consciousness of <30 minutes duration, b. Glascow Coma Scale (GCS) ≥ 13, and c. Symptoms and/or signs diagnostic of concussion)²⁵
- Diagnosis of mTBI ≥3 months and ≤2 years at the time of study enrollment
- Suffering from CPTH of any etiology (e.g. tension or migraine), with chronic defined as developed within 7 days after injury and lasting ≥3 months from the time of injury²⁵

5.2 EXCLUSION CRITERIA

An individual who meets any of the following criteria will be excluded from participation in this study:

- Non-English speaking
- Participation in acupuncture treatment outside of the study, while enrolled
- History of pre-existing primary headache, defined as more than 12 days of tension-type headache annually and/or more than one migraine attacks per month in the last year⁴
- History of any other serious neurological, psychiatric, chronic pain disorders, or seizures
- History of bleeding diathesis, other bleeding disorders, or syncope with needle puncture
- History of cardiac arrhythmia or current pacemaker, neurostimulator, or other implanted stimulation device
- Recent or active substance use disorder
- Women who are currently pregnant, lactating, or planning to become pregnant during the study
- Any other medical conditions that could affect their ability to participate in acupuncture treatments for the study duration (as determined by study investigators)
- Active participation or past participation ≤3 months in any other interventional study.
- Unwilling to participate in all study related activites

5.3 LIFESTYLE CONSIDERATIONS

N/A

5.4 SCREEN FAILURES

Pre-screening Phone Call:

All potential participants will undergo a pre-screening phone call to determine whether they meet the inclusion/exclusion criteria. Patients will be considered ineligible if they do not meet one or more of the inclusion/exclusion criteria during pre-screening. We will collect information on why participants are ineligible or decide not to move forward with the trial.

Pre-treatment Visit:

Screen failures are defined as participants who are considered eligible during the pre-screening phone call, but it was subsequently determined that they do not meet one or more of the inclusion/exclusion criteria at or after the Pre-treatment (baseline) visit. We will collect information on why participants screen fail or decide not to move forward with the trial.

Rescreening Patients:

Individuals who do not meet the criteria for participation in this trial (ineligible or screen failure) because of meeting one or more exclusion criteria that are likely to change over time may be rescreened up to one time. Examples include: successful treatment for a substance use disorder; women who are no longer pregnant, lactating, or planning to become pregnant; or participation in an interventional study≥3 months prior. Rescreened participants will be assigned a new participant number.

5.5 STRATEGIES FOR RECRUITMENT AND RETENTION

Recruitment: Individuals with mTBI suffering from CPTH will be recruited by physician and therapist referrals from HealthPartners' clinics. We will also advertise our research study by distributing flyers to HealthPartners' physicians and throughout HealthPartners' clinics. Recruitment flyers will also be provided to our community partners for example, the Minnesota Brain Injury Alliance, TRIA, and Allina Health. If we encounter difficulties with recruitment, we plan to submit an amendment to the IRB to contact HealthPartners patients and members and invite them to participate.

To reach our target enrollment, we anticipate that we will need to screen 100 people, of those 50 individuals will sign the informed consent, and of those 40 individuals will be randomized to treatment groups. We expect that we will enroll approximately 35% (~13) women and 65% (~23) men, primarily between the ages of 41-84, and approximately 80% will be white. Values are based on our Regions Hospital Rehabilitation census data.

Remuneration: Participants will be provided gift cards totaling \$50 per person for completing certain time points of the research study. Specifically, after completing all acupuncture treatment visits, participants will receive a \$25 gift card. After completion of the 12-week post-treatment visit (end of study visit) participants will receive another \$25 gift card.

6 STUDY INTERVENTION(S) OR EXPERIMENTAL MANIPULATION(S)

6.1 STUDY INTERVENTION(S) OR EXPERIMENTAL MANIPULATION(S) ADMINISTRATION

6.1.1 STUDY INTERVENTION OR EXPERIMENTAL MANIPULATION DESCRIPTION

The study intervention for both groups is acupuncture treatment. Acupuncture is a treatment where fine needles are inserted into specific areas of the body to achieve a therapeutic benefit. The treatment regimen is described next in more detail.

6.1.2 ADMINISTRATION AND/OR DOSING

Acupuncture Treatment Methods:

Group 1 will receive weekly acupuncture and Group 2 will receive twice-weekly acupuncture over five weeks. Acupuncture treatments will be separated by a minimum of 2 days and a maximum of 14 days, unless a participant has an illness, such as COVID-19. In this case, additional time may be allowed, as determined by the investigator. Treatment methods will be identical for both groups and are described below.

Standard, sterile stainless-steel, disposable needles (DongBang™ Corporation, Spring Ten 0.25x30mm; Boryeoung, Republic of Korea) will be inserted in the acupuncture point locations (described below), with a total of 18 needles used for each treatment session. The depth of the needle insertion will be approximately 10-20mm, depending on the region of the body undergoing treatment. Needle reaction (soreness, numbness or distended feeling around the point, also known as a Deqi sensation) will occur during the initial insertion. Following 10 minutes of retention, all needles (except points St36 and LI4 under electrostimulation, and auricular points SM and PtZ) will be rotated in order to maintain Deqi sensation. Maintaining Deqi sensation has been shown to increase the effectiveness of acupuncture. All needles will be left in place for a total of 30 minutes, which is a typical duration in acupuncture practice. It also is a common duration of previously reported clinical trials of acupuncture for headaches and migraines. 11,12,28

Acupuncture points were selected for their classical indications, anatomical locations, effect on pain networks^{29,30} and influence on cerebral blood flow.³¹ The anatomical location for each point will be based on the World Health Organization's acupuncture point guideline.³² Electroacupuncture will be administered with Pantheon Research electrostimulation 8c pro machines (Pantheon Research Inc; Huntington Beach, CA), with a continuous milliampere wavelength of 2Hz at stomach 36 (ST36) and large intestine 4 (LI4). The intensity will be gradually increased to a comfortable level that participants can tolerate, without the sensation of pain. Traditional Chinese manual acupuncture will be used at eight acupuncture points: yin tang (YT) and Du20 and bilateral acupuncture of liver 3 (LV3), urinary bladder 2 (UB2), small intestine 19 (SI19), extra point Anmian (EX-22), and two auricular points Shen Men (SM) and point zero (PtZ). During treatment, acupuncture needles or electrical stimulation can be removed due to extreme pain or discomfort, so as not to exceed the removal of more than 2 of the 18 needles.

6.2 FIDELITY

6.2.1 INTERVENTIONIST TRAINING AND TRACKING

Acupuncturists:

Acupuncture treatments will be administered by MN licensed acupuncturists with a Master's degree level of training in acupuncture (or higher) from accredited institutions, and five or more years of clinical experience. Prior to enrolling participants, the acupuncturists will complete practice sessions together of the treatment protocol and methods of administration to ensure consistency between providers

Training:

Following IRB approval and prior to recruitment and enrollment, the study acupuncturists will complete 10 practice sessions. For the training, we will seek 12 volunteers who will sign a volunteer consent form prior to participating. The purpose of training will be to ensure consistency in intervention procedures and further standardized treatment methods. This includes, but is not limited to: needle location (18 points), needle depth, time of first and last needle placement, total treatment duration, and pre-defined electro-acupuncture settings.

Tracking:

All practice sessions will be documented on a training log. This will include dates and times of the trainings, names of the volunteers, and printed names and signatures of the study acupuncturists. We will also keep a record of the volunteers' signed treatment release forms.

6.3 MEASURES TO MINIMIZE BIAS: RANDOMIZATION AND BLINDING

Randomization:

Randomization will be performed with a 1:1 allocation ratio. Balanced treatment assignments will be achieved using permuted block randomization with random block sizes stratified by gender. This decision was based on evidence that females in this population reported higher rates of headaches.³³ The study biostatistician will generate a randomization schedule using the SURVERYSELECT procedure in SAS. Assignments will not be seen by other study personnel in advance and will not be changed after randomization.

Blinding:

Study personnel will be unblinded to the randomization, as it will be clear the number of participants who receive 5 acupuncture treatments versus those that receive 10. In addition, it will be clear to participants which treatment group they are in and it will be impossible to blind them from this information.

6.4 STUDY INTERVENTION/EXPERIMENTAL MANIPULATION ADHERENCE

Participants will be asked to adhere to study visits and to complete study assessments. Participants will remain active unless withdrawn from the study (see **Section 7**). We will track participants' adherence to study visits, as well as completion of the assessments. These will be documented in the relevant eCRF.

6.5 CONCOMITANT THERAPY

For this protocol, participants may use non-opioid analgesics for pain control, including over-the-counter medications and dietary supplements, and prescribed medications. This includes use for rescue therapy in the event of exacerbation of symptoms due to acupuncture treatment. Medication usage will be assessed at each study visit and documented in the relevant eCRF.

6.5.1 RESCUE THERAPY

Any medications used for rescue therapy will be recorded in the Headache Diary.

7 STUDY INTERVENTION/EXPERIMENTAL MANIPULATION DISCONTINUATION AND PARTICIPANT DISCONTINUATION/WITHDRAWAL

7.1 DISCONTINUATION OF STUDY INTERVENTION/EXPERIMENTAL MANIPULATION

When a participant who signed the consent form chooses to discontinue participation in the study or study intervention, or if the principal investigator and co-investigators determine that a participant should discontinue participation, they will be withdrawn from the study. A withdrawal will either be defined as 'Patient Withdrawal' or 'Principal Investigator Withdrawal'. The participant will be asked to complete an early withdrawal phone call 7-14 days from the date the intervention was discontinued. The purpose of the phone call will be to record any AEs or serious adverse events (SAEs) that may have occurred after the discontinuation of treatment. Research staff will attempt to call the participant up to 3 times.

The data that will be collected at the time of study withdrawal will include the following:

The reason(s) for discontinuation of the study intervention

The data that will be collected during the early withdrawal phone call will include the following:

AEs or SAEs that occurred since the time of withdrawal

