 - © E-mail the Pittsburgh Sleep Quality Index (PSQI) and Traumatic Brain Injury-Quality of Life (TBI-QOL) surveys to the patient for completion. Ask patients to complete the surveys prior to their first acupuncture visit. During the reminder call for the acupuncture visit, patients will be reminded to complete the surveys if they have not yet completed them.
 - Provide participants instructions regarding the Headache Diary REDCap survey (example script below):
 - "You will receive a Headache Diary survey via e-mail once a week for the next 4 weeks. Each survey will ask questions about your headaches over the last week. What is most important for you to remember is the number of headaches you had. The rest of the information is also helpful."
 - 2. Provide participants a paper diary and ask them to use it to keep track of their headaches during the week. Instruct participants that they should use it to fill out the weekly e-mail survey.
 - 3. Show participants an example of the REDCap survey.

3. Study Intervention

- Duration: Each visit approximately 1 hour
- A study acupuncturist will:
 - Complete the Adverse Events (AE) Reporting, Medication Review, and Treatment Adherence in the relevant eCRFs in REDCap.
 - o Perform the acupuncture treatment.
- Only at the LAST acupuncture visit, a study acupuncturist will:
 - Provide participants instructions regarding the Headache Diary REDCap survey (example script below):
 - "Like you experienced before, you will receive a Headache Diary survey via e-mail once a week for the next 4 weeks. Each survey will ask questions about your headaches over the last week. What is most important for you to remember is the number of headaches you had. The rest of the information is also helpful."

2. Provide participants a paper diary and ask them to use it to keep track of their headaches during the week. Instruct participants that they should use it to fill out the weekly e-mail survey.

3. Show participants an example of the REDCap survey.

4. 4-week Post-treatment Visit

- Duration: Approximately 30 minutes via phone
- Research staff will:
 - Complete the AE Reporting and Medication Review forms in the relevant eCRFs in REDCap.
 - o E-mail the PSQI and TBI-QOL surveys to the patient for completion. Ask patients to complete the surveys within one week. Five days after the visit, patients will receive a reminder call if they have not yet completed the surveys.

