7.2 PARTICIPANT DISCONTINUATION/WITHDRAWAL FROM THE STUDY

Participants are free to withdraw from participation in the study at any time upon request. An investigator may discontinue a participant from the study for the following reasons:

- 1. Participant has not completed an acupuncture treatment for > 14 days, unless a participant has an illness, such as COVID-19. In this case, additional time may be allowed, as determined by the investigator.
- 2. Significant study intervention non-compliance
- 3. Lost-to-follow up; unable to contact subject (see Section 7.3, Lost to Follow-Up)
- 4. Any event or medical condition or situation occurs such that continued collection of follow-up study data would not be in the best interest of the participant or might require an additional treatment that would confound the interpretation of the study
- 5. The participant meets an exclusion criterion (either newly developed or not previously recognized) that precludes further study participation

The reason for participant discontinuation or withdrawal from the study will be recorded on the relevant eCRF. Subjects who sign the informed consent form and are randomized but do not receive the study intervention may be replaced. Subjects who sign the informed consent form, and are randomized and receive the study intervention, and subsequently withdraw, or are discontinued from the study, will not be replaced.

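### Stopping acupuncture is treated as withdrawal from the study, which leaves no planned route to the 4-week diary, so these participants drop out of a primary analysis described as intention-to-treat

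*Combined protocol and SAP*

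**What the plan says.** Section 7.1 has two triggers and one consequence. The participant's trigger is worded "When a participant who signed the consent form chooses to discontinue participation in the study or study intervention". The investigators' trigger and the consequence follow: "if the principal investigator and co-investigators determine that a participant should discontinue participation, they will be withdrawn from the study". The consequence is mandatory, and stopping the intervention alone is enough to bring it about.

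Section 7.2 adds reasons for which an investigator may discontinue someone from the study. Item 1 is "Participant has not completed an acupuncture treatment for > 14 days, unless a participant has an illness, such as COVID-19"; item 2 is "Significant study intervention non-compliance". Item 1 mirrors the dosing rule in 6.1.2: "Acupuncture treatments will be separated by a minimum of 2 days and a maximum of 14 days".

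For data after withdrawal, 7.1 lists the reason for stopping and, from one phone call at 7-14 days, "AEs or SAEs that occurred since the time of withdrawal". Headache days are not on the list. In section 1.3 the post-treatment diary instructions and paper diary are given only at the last acupuncture visit, with the script "Like you experienced before, you will receive a Headache Diary survey via e-mail once a week for the next 4 weeks".

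Section 9.3 puts all analyses on an intention-to-treat basis. Section 9.4.2 says the same, whatever treatment was received, but admits to the final analysis only participants with complete pre-treatment and 4-week post-treatment data.

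**The concern.** Read together, these sections do not deliver the stated analysis. A participant who stops acupuncture partway is withdrawn, has no planned 4-week headache count, and then fails the complete-data condition. Early stoppers are the people for whom an intention-to-treat result and a complete-case result can differ.

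The other planned analyses do not fill the gap. The per-protocol analysis leaves poor attenders out by design. The mixed model has at most their pre-treatment diary. The baseline comparison in 9.4.2, made if much data are missing, recovers no headache days. The delay analysis in 9.4.9 covers delays due to illness only. No imputation of the primary endpoint is planned. Staff who decide on withdrawal under 7.2 know the assigned arm (6.3).

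What is at stake is selective loss of the primary outcome, with no later means of judging what that loss did to the comparison of 5 with 10 sessions.

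**Working it through.** **Inputs from the plan.** Standard deviation 4.47 and planned difference 4.5 days (9.2); two-sided two-sample t-test at 5% (9.2); 1:1 allocation (6.3); enrolment of 40 (1.1, 10.4), hence 20 per arm.

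**Inputs assumed.** Withdrawals of 4 of 40 (the rise from 36 to 40 offsetting them one for one) or 8 of 40 (down to the N = 32 row of the power table). Withdrawn participants would have improved D = 2 to 4.5 days less than the rest, the upper end being the whole planned effect. The documents give no figure for the count, the arm split or D.

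**The plan's own figures.** Exact power from the noncentral t distribution with SD 4.47 and difference 4.5 is 0.835 at N = 36, 0.787 at N = 32, 0.758 at N = 30 and 0.727 at N = 28. All match the table in 9.2, so nothing is wrong with the stated power on this point.

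**Shift in the arm contrast.** If w of 20 in an arm are lost and would have improved D days less, the completers' mean improvement exceeds that of all 20 by D × w/20. The contrast therefore shifts by

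D × (wA − wB)/20,

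in favour of the arm that loses more. The standard error is 4.47 × √(1/n1 + 1/n2). Type I error comes from the noncentral t with noncentrality shift/SE, assuming no true difference among all randomised.

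| Lost, arm A vs arm B | Analysed | SE | Shift at D = 2 | Shift at D = 4.5 | Type I error, D = 2 to 4.5 |
|---|---|---|---|---|---|
| 2 vs 2 | 18/18 | 1.490 | 0 | 0 | 5.0% |
| 3 vs 1 | 17/19 | 1.492 | 0.20 | 0.45 | 5.2 to 6.0% |
| 4 vs 0 | 16/20 | 1.499 | 0.40 | 0.90 | 5.8 to 9.0% |
| 4 vs 4 | 16/16 | 1.580 | 0 | 0 | 5.0% |
| 5 vs 3 | 15/17 | 1.583 | 0.20 | 0.45 | 5.2 to 5.9% |
| 6 vs 2 | 14/18 | 1.593 | 0.40 | 0.90 | 5.7 to 8.5% |

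The largest ratio is 0.90/1.499 = 0.60 SE, and 0.90/4.5 = 20% of the planned effect. Splits of eight more uneven than 6 vs 2 are not tabulated.

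If the outcome gap exists in one arm only, an even split also shifts the contrast, by D × w/20: 0.20 to 0.45 day at 2 vs 2 and 0.40 to 0.90 day at 4 vs 4.

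**Would follow-up fit the schedule?** Take weekly sessions on days 0, 7, 14, 21, 28 and twice-weekly sessions on days 0, 3, 7, 10, 14, 17, 21, 24, 28, 31, counted from the first session. If the diary starts on the scheduled date of the last session, it starts 7 to 28 days (weekly) or 3 to 31 days (twice weekly) after the last session attended. The schema places the first session on Day 29 to 43 (29 + 14). The 4-week call then falls on Day 29 + 28 + 28 = 85 to 43 + 28 + 28 = 99 (weekly) or 29 + 31 + 28 = 88 to 43 + 31 + 28 = 102 (twice weekly). Day 85-102 lies inside the schema's Day 71-106 + 7.

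Instructions must not wait for the 14-day limit. The first survey is due on day 35 (weekly) or 38 (twice weekly). The limit passes only on day 36 after weekly session 4, and on days 39 and 43 after twice-weekly sessions 8 and 9. The missed visit itself falls on day 28 (weekly), or on days 28 and 31 (twice weekly), which is in time.

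**The case against.** The strongest reply is that loss of the diary is inferred. No sentence forbids collecting it. Section 8.1 describes e-mailed surveys in three 4-week periods without tying them to a final session, and participants already know the diary from the pre-treatment period. That stands: a reader might infer that the protocol bars the diary after withdrawal, and it does not. It provides no route to it, and leaves it off an explicit list of what is collected.

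The plan also limits how often this arises. Section 7.2 is permissive and excepts illness, 7.3 requires rescheduling and counselling after a missed visit, and 6.4 states "Participants will remain active unless withdrawn from the study". A poor attender who is not withdrawn and keeps the diary is analysed as randomised. Withdrawn participants still count in the adverse-event, adherence and baseline summaries. All this reduces the number affected. It does not help someone who stops, because 7.1 is mandatory.

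A reader might take the version 11 entry, which raised enrolment to 40 because of withdrawals, as proof that people stopped acupuncture and were lost in this way. The entry gives neither timing nor reason. Randomisation takes place at Visit 1 and treatment starts around Day 29, so some may have left before any session. An amendment could not recover past diaries in any case.

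A further tempting inference is that the common 14-day limit removes more people from one arm. No document gives rates by arm, so that is speculation. Section 8.3.9 likewise withdraws participants who become pregnant during the course, but the protocol gives a hormonal reason for excluding pregnancy, and that rule is left alone here.

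**Conclusion.** The inconsistency is in the text: for participants withdrawn during the course, the data-collection rules in 7.1 and 7.2 cannot supply the intention-to-treat analysis promised in 9.3 and 9.4.2. It should be corrected, because it affects the primary endpoint and a missed prospective diary cannot be rebuilt later.

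Its size is unknown and may be nil. With 4 to 8 of 40 lost and a gap of 2 to 4.5 days, the contrast is unmoved by an even split with the same gap in both arms. It moves 0.2 to 0.45 day at 3 vs 1 or 5 vs 3, with type I error of 5.2 to 6.0%. The 0.9 day and 9.0% at 4 vs 0 need every loss in one arm and a gap as large as the whole planned effect, so they should not be read as the expected error rate. The direction is unknown.

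This is a point about bias, not power: a reader might infer that the trial is underpowered, but the plan's power figures reproduce and 9.2 already tabulates attrition.

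**What to change.** - **7.1:** define stopping acupuncture and leaving the study as separate events, and withdraw only those who leave the study.
- **7.2:** make items 1 and 2 reasons to stop acupuncture only. Record a gap beyond the limit in 6.1.2 as a protocol deviation.
- **Follow-up:** keep willing participants in the e-mailed diaries and the 4- and 12-week phone visits. Fix the diary start in advance, for example as the scheduled date of the last session, set at the first session. Give the instructions on the call that 7.3 already requires after a missed visit.
- **Analysis and reporting:** analyse these participants in the assigned arm. Report by arm how many stopped, why, and how many supplied the 4-week diary.
- **9.4.9:** extend the delay sensitivity analysis to early stopping and to delays for any reason.

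The cost is one IRB amendment, matching edits to the consent form and early withdrawal script, one REDCap survey rule, and a few more e-mails and calls. No new visit window is needed. The drawback is that early stoppers start the diary 3 to 31 days after their last session, against 0 for completers, and that some under-treated participants enter the primary analysis. Intention-to-treat implies the second, and the extended 9.4.9 analysis shows the result without them.

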8.3.4 TIME PERIOD AND FREQUENCY FOR EVENT ASSESSMENT AND FOLLOW-UP

The occurrence of an AE or SAE may come to the attention of study personnel during study visits and interviews of a study participant.

All AEs, not otherwise precluded per the protocol, will be captured on the appropriate eCRF. Information to be collected includes event description, time of onset, clinician's assessment of severity, relationship to study procedures (assessed only by those with the training and authority to make a diagnosis), and time of resolution/stabilization of the event. All AEs occurring while on study will be documented appropriately regardless of relationship. All AEs will be followed to adequate resolution.

Any medical or psychiatric condition that is present at the time that the participant is screened will be considered as baseline and not reported as an AE. However, if the study participant's condition deteriorates at any time during the study, it will be recorded as an AE.

Changes in the severity of an AE will be documented to allow an assessment of the duration of the event at each level of severity to be performed. Documentation of onset and duration of each episode will be maintained for AEs characterized as intermittent.

Study staff will record events with start dates occurring any time after the first acupuncture treatment session until the 12-week post-treatment visit. At each acupuncture treatment visit (after the 1st) and the 4-week and 12-week post-treatment visits, study staff will inquire about the occurrence of AE/SAEs since the last visit. All reported events will be monitored until the 12-week post-treatment visit. Any reported event that is definitely or probably related to the intervention will be followed until resolution or stabilization.

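### Section 7.1 gives two look-back starts for the early-withdrawal safety call, and no enquiry about new adverse events is scheduled after it

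*Combined protocol and SAP*

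**What the plan says.** Section 7.1 withdraws from the study anyone who stops, including a participant who stops only the acupuncture. Two data collections follow.

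- At withdrawal, the only item listed is "The reason(s) for discontinuation of the study intervention".
- Afterwards there is one call, timed as follows: "The participant will be asked to complete an early withdrawal phone call 7-14 days from the date the intervention was discontinued". Staff try up to three times. The paragraph says the call is to record AEs or SAEs "that may have occurred after the discontinuation of treatment". The list of data to be collected at that call reads "AEs or SAEs that occurred since the time of withdrawal".

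Section 7.2, reason 1, lets an investigator discontinue a participant when "Participant has not completed an acupuncture treatment for > 14 days", with more time allowed for illness.

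Section 8.3.4 sets the general AE window, which runs from after the first session to the 12-week post-treatment visit. At each session after the first, and at the 4- and 12-week visits, "study staff will inquire about the occurrence of AE/SAEs since the last visit". The section also states: "All AEs will be followed to adequate resolution". It has reported events monitored up to the 12-week visit, and definitely or probably related ones followed until they resolve or stabilise. Section 8.3.9 uses the same call for pregnancy withdrawals and gives no look-back start.

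Section 9.4.3 reports, by arm, the proportion with at least one AE/SAE, with odds ratios and 95% confidence intervals.

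**The concern.** The routine enquiries form a chain: each reaches back to the previous visit, so from the first session onward no time is left unasked. Withdrawal breaks the chain. Nothing about AEs is listed for the withdrawal contact, and the data list for the call starts the clock at withdrawal, not at the last attended visit. The two descriptions of the call within 7.1 also disagree. A participant who stops after the first session has had no look-back enquiry at all before the call.

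Safety and tolerability are Specific Aim 2 and a secondary endpoint, and Section 10.1.6 says there is no data safety monitoring board. If withdrawn participants are asked about less time than completers, their recorded AE frequency will be lower for that reason alone. If withdrawals differ by arm, the comparison of 5 with 10 sessions could be distorted. This is separate from the loss of headache-diary data after withdrawal.

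**Working it through.** The plan gives no figure of its own on this point, so the check compares the sections and counts days. Let day 0 be the last attended session and W the day of withdrawal.

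1. **Look-back under the data list.** The call asks about day W onward, and at W only the reason is taken. The unasked interval runs from day 0 to day W. If W = 0 there is little or no gap. Under 7.2 reason 1 the participant must have gone more than 14 days without treatment, so W is at least 14 + 1 = 15.

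2. **The 7-14 day window under 7.2 reason 1.**
   - Counted from the last session, it runs from day 7 to day 14 and closes before day 15, the earliest withdrawal.
   - Counted from withdrawal, it runs from 15 + 7 = day 22 to 15 + 14 = day 29. The data list then covers day 15 onward and omits the first 15 days. For W = 21 the call falls on days 28-35 and 21 days are omitted.

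3. **Does the purpose sentence close the gap?** It does if treatment counts as discontinued at the last session. On that same date, however, the call window has expired (step 2). If discontinuation means the withdrawal date, the window works, but the purpose sentence also starts at day W. So in the reason 1 case no single meaning of the date makes both the look-back and the window work.

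4. **When new-event collection ends.** The post-treatment window for completers is 12 × 7 = 84 days. For withdrawal during treatment with the intervention ending at the last session (W = 0), the call comes on day 7-14:
   - 7/84 = 8.3% and 14/84 = 16.7% of the window is asked about.
   - 84 − 14 = 70 to 84 − 7 = 77 days have no scheduled enquiry about new events.

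   Under reason 1 with the window counted from withdrawal at day 15, a full look-back to day 0 would reach 22/84 = 26.2% to 29/84 = 34.5%. The data list still gives only 7-14 days.

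5. **Weight in the endpoint.** With 40 randomised 1:1, an arm holds about 20. One participant whose only AE is missed moves the arm's proportion by 1/20 = 5 percentage points, and two move it by 10.

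6. **Illustration, on an assumption.** The documents give no AE rate for this population. If the risk of a first event over the 84 days is p with constant hazard, the chance that it falls within the first 14 days is 1 − (1 − p)^(14/84). For p = 10%, 30% and 50% this is 1.7%, 5.8% and 10.9%. Constant hazard is doubtful here. The commoner effects listed in 2.2.1, such as bleeding, haematoma and bruising, are tied to needling and should appear early. Early clustering makes the late truncation in step 4 matter less and the gap in step 1 matter more.

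**The case against.** The strongest reply is that the purpose sentence in 7.1 already covers events after treatment stops, and that the early-withdrawal call script listed in 10.1.1.1, which is not in the documents, may ask the right question. This stands as far as it goes. A reader might infer that events between the last session and withdrawal are never asked about, but the documents do not support that. They contradict each other, and the gap arises only if the data list governs and withdrawal is later than the last session.

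A reader might also infer that the call is the last contact. No section says so. Section 8.3.4 has already reported events monitored to the 12-week visit, and definitely or probably related ones beyond it if needed, without exempting withdrawn participants. What is cut short is the enquiry about new events.

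It can fairly be said that a reaction that caused the stop is likely to surface as the recorded reason, and that 7.3 requires contact after a missed visit. Neither is an AE enquiry as written, but both weaken any claim that those who stop because of a reaction are missed altogether.

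The amendment history in 10.4 says enrolment rose to 40 because of withdrawals. It is tempting to conclude that participants were affected. The entry gives no timing, reason or treatment status, and 7.2 recognises that some randomised people may never be treated.

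Finally, 9.4.3 plans no inferential statistics on these outcomes and has no rule that withdrawn participants count as event-free. The latter is what follows by default if they stay in the denominator with nothing recorded. Odds ratios with confidence intervals still invite a comparison of the arms.

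**Conclusion.** The point holds in a limited form. Section 7.1 contradicts itself on where the call's look-back begins. Followed as listed, it leaves unasked the time from the last attended visit to withdrawal, which is at least 15 days under 7.2 reason 1. In that case a 7-14 day window counted from the last session cannot be met. New-event enquiry is scheduled for about 7-14 of 84 post-treatment days (8.3% to 16.7%) when withdrawal occurs during treatment and the intervention ends at the last session.

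The consequence for 9.4.3 is unequal observation time between withdrawn participants and completers. Distortion between arms is conditional on withdrawals differing by arm, on which the documents are silent. The size of any bias cannot be stated, because neither the AE rate nor the number and timing of withdrawals is given. The conclusion does not rest on the assumed risks in the illustration. Confidence is medium, because the script could resolve the look-back question. The plan should be changed on this point, at small cost.

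**What to change.** - In the 7.1 data list, replace the starting point with: *since the last attended study visit, including the status of any AE open at that visit*. Ask this at withdrawal, where contact is made, and again at the call. Bring the call script into line.
- Reconcile 7.1, 7.2 and 8.3.4 on which date starts the 7-14 day window and on when AE collection ends for withdrawn participants. The choice of date is for the investigators; the sections need to agree.
- For treated participants who stop but agree to safety contact, keep the existing 4- and 12-week AE phone enquiries.
- In 9.4.3, report AE observation time by arm for those who withdrew, so that the proportions and odds ratio can be read against it.

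The cost is a few lines of text, one script revision, and up to two short calls per withdrawn participant who agrees. Some will decline, so observation time will remain unequal to some degree, which is why it should be reported.
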